### Summary Table of Study Protocol

Title	Postmarketing Surveillance Study for Kyprolis® (carfilzomib) in Korea (study number 20160117)
Protocol version identifier	Final version 1.0
Date of last version of the protocol	29 March 2016
EU Post Authorisation Study (PAS) Register No	
Active Substance	carfilzomib
Medicinal Product	Kyprolis®
Product Reference	NA
Procedure Number	
Sponsor	Amgen Korea
Joint PASS	No
Research Question and Objectives	To assess safety and effectiveness of Kyprolis® in post-marketing real-life setting
Country(-ies) of Study	Korea
Author	[REDACTED] Sr. medical advisor, region (Asia) Amgen

Approved

### Study Design Schema

1. Patient with multiple myeloma who have received at least on prior therapy.
2. KRd (Kyprolis (carfilzomib), Revlimid (lenalidomide) and low-dose dexamethasone) or Kd (Kyprolis (carfilzomib) and low-dose dexamethasone) administered on D1, 2, 8, 9, 15, 16 per cycle, 1 cycle: 28 days (Refer to [Table 1](#) and [Table 2](#) for details).

Approved

## 2. List of Abbreviations

Abbreviations	Definition of the Terms
ADR	Adverse Drug Reaction
AE	Adverse Event
CRF	Case Report Forms
CI	Confidence Interval
CR	Complete Response
sCR	stringent Complete Response
CRO	Contract Research Organization
DBP	Diastolic Blood Pressure
ECOG	Eastern Cooperative Oncology Group
FLC	Free Light Chain
HR	Hazard Ratio
ICMJE	International Committee of Medical Journal Editors
IMWG	International Myeloma Working Group
INN	International Nonproprietary Name
IRB	Institutional Review Board
ISS	International Staging System
IV	Intravenous(ly)
KIDS	Korea Institute of Drug Safety and Risk Management
Kd	Kyprolis (carfilzomib) and low-dose dexamethasone
KRd	Kyprolis (carfilzomib), Revlimid (lenalidomide) and low-dose dexamethasone
K-RMP	Korea Risk Management Plan
MFDS	Ministry of Food and Drug Safety
ORR	Overall Response Rate
PFS	Progression-Free Survival
PMS	Post Marketing Surveillance
PR	Partial Response
Rd	Revlimid (lenalidomide) and low-dose dexamethasone
SAE	Serious Adverse Event
SBP	Systolic Blood Pressure
SD	Standard Deviation
TTP	Time to Progressive
VGPR	Very Good Partial Response
Vd	Velcade (Bortezomib) and low-dose dexamethasone

Approved

### 3. Responsible Parties

Sponsor: Amgen Korea

Investigators: Investigators at medical institutions with active contracts for this study, Korea.

### 4. Abstract

- Study Title

Postmarketing Surveillance Study for Kyprolis® (Carfilzomib) in Korea

- Study Background and Rationale

According to local regulation, a regulatory post-marketing surveillance study is required for new medicines approved in Korea to collect safety and effectiveness data in routine clinical practice.

Korea Risk management plan (K-RMP) of Kyprolis® includes this study as a part of pharmacovigilance plan.

- Research Question and Objective

- Primary Objective

The primary objective of this study is to determine the incidence of adverse events (AEs), serious AEs and adverse drug reactions (ADRs) among patients with at least 1 prior therapy receiving Kyprolis® in real-life setting in its registered indication(s) as required by MFDS. Kyprolis is indicated in combination with lenalidomide and dexamethasone or just with dexamethasone for the treatment of patients with multiple myeloma who have received at least one prior therapy.

- Secondary Objective

The secondary objective of this study is to investigate effectiveness of Kyprolis® (Overall Response Rate).

- Hypothesis(es) / Estimation

There is no hypothesis to be tested. Instead, the proposed study will provide descriptive data on real-life use of Kyprolis® and adverse event occurrence in patients in Korea.

- Study Design/Type

Prospective observational study in post marketing setting without a comparator arm

- Study Population or Data Resource

Patients for whom Kyprolis® is prescribed at participating medical institutions in accordance with the approved Korea prescribing information (Kyprolis is indicated in combination with lenalidomide and dexamethasone or just with dexamethasone for the

Approved

treatment of patients with multiple myeloma who have received at least one prior therapy).

The investigator, or a person designated by the investigator will collect the patient's data using the case report forms (CRF) authorized by Amgen Korea. The patient's information needed for analysis and reporting will be entered/transmitted into the validated database or data system. Study data management will be performed according to applicable standards and data cleaning procedures. The database will be locked once the quality control procedures are completed. The original CRFs will be retained by Amgen Korea. The final data collection for each patient will be performed at the time point of 24 weeks (6 cycles) or drop-out. Most of major severe AE should be detected within 6 cycles based on ASPIRE study.

- Summary of patient eligibility criteria

Inclusion criteria: A patient can be included into the study only if all of the following criteria are met:

1. Signed and dated informed consent
2. Patients diagnosed with multiple myeloma who have received at least one prior therapy
3. Patients who are prescribed with Kyprolis® (in combination with lenalidomide and dexamethasone or in combination with dexamethasone) for the first time

Exclusion criteria: All contraindications specified in the local product information have to be considered. In addition, patients treated with any regimens not specified in the approved prescribing information of Kyprolis® in Korea should be excluded from the study.

- Follow-up

- The total follow-up period is 24 weeks.
  - Safety assessment will be performed at 4 weeks, 8 weeks, 12 weeks and 24 weeks.
  - Response assessment will be performed at 12 weeks and 24 weeks.
- The study protocol does not define exact referral dates for follow-up visits. Follow-up visits occur during routine practice. The investigator documents the date of initial visit and follow-up in the case report form and follows the study procedures (usually pertaining to data collection only) for the visit.

Approved

- Variables
  - *Outcome Variables*
    - Patient demographics and medical history
    - Diagnostic information
    - Prior and Concomitant medication
    - Prior anti myeloma therapy
    - Myeloma characteristics eg, cytogenetic risk
    - Safety: Adverse events (AEs) including serious adverse events and adverse drug reactions (ADRs)
    - Effectiveness: Overall response rate (ORR, %) according to the International Myeloma Working Group (IMWG) uniform response criteria to assess the tumor response (sCR, CR, VGPR, or PR) ([Appendix F](#))
    - Laboratory values

- Study Sample Size

The sample size will be 700 patients (at least 600 patients required for safety analysis according to local regulation).

- Data Analysis

Patient demographics, baseline characteristics, medical history and concomitant drug use will be summarized. For the safety analysis, adverse event will be presented using the number of treated patients, incidence proportion and number of patients with events. For the effectiveness analysis, overall response rate at 12 and 24 weeks after drug administration will be analysed.

## 5. Amendments and Updates

None.

## 6. Milestones

The given period of re-examination is 6 years from the time of product approval obtained as a new medicine in Korea.

Regular interim reports should be submitted to MFDS every 6 months for the first 2 years and annually afterward during the period of re-reexamination. The due date for submission of each regular interim reports date will be determined depending on the approval date of Kyprolis® in Korea.

The re-examination report (ie, the final study report) will be prepared and submitted to MFDS within the specific timeline, in three months after completion of re-examination period, according to local regulation.

## 7. Rationale and Background

### 7.1 Diseases and Therapeutic Area

Multiple myeloma is an incurable and fatal plasma cell malignancy and is the second most common lymphoid malignancy worldwide [1],[2]. Three drugs that have been commonly treated to patients with relapsed multiple myeloma are lenalidomide (Revlimid, R), an IMiD; bortezomib (Velcade, V), a proteasome inhibitor; and liposomal doxorubicin (in combination with bortezomib)[3]. There is significant room for improvement as none of these agents have been reported to extend median disease-free intervals (PFS or TTP) past 14 months in large, registrational Phase 3 trials [4]-[6].

As of 19 January 2016, Overall, an estimated 3040 subjects (2522 subject-years) have been exposed to carfilzomib in clinical trials conducted by Onyx since the beginning of the development program. The results from the PX-171-009 (ASPIRE) study demonstrated that Kyprolis® may provide an important treatment option for patients with relapsed multiple myeloma. This Phase 3 study was a randomized, open-label, multicenter study comparing 2 treatment regimens (carfilzomib, lenalidomide, low-dose dexamethasone ["KRd"] versus lenalidomide, low-dose dexamethasone ["Rd"]) for patients with relapsed multiple myeloma with 1 to 3 prior therapies. A total of 792 patients were enrolled (396 per arm). The trial demonstrated that Kyprolis® improved progression-free survival (PFS) with a hazard ratio (HR) of 0.69 (95% confidence interval [CI]: 0.57, 0.83;  $p < 0.0001$ ). The patients in the KRd treatment arm had a significantly longer duration of PFS than did the patients in the Rd arm, with a median PFS duration of 26.3 months (95% CI: 23.3, 30.5) versus 17.6 months (95% CI: 15.0, 20.6), respectively—a difference of 8.7 months at the median.

In addition, the results from Phase 3 study 2011-003 (ENDEAVOR) in relapsed multiple myeloma demonstrated superiority of Kd (Kyprolis (carfilzomib) and low-dose dexamethasone) over Vd (Velcade (Bortezomib) and low-dose dexamethasone), a current standard of care for this patient population, based on a 9.3 month improvement in PFS for those randomized to Kd (median PFS 18.7 months versus 9.4 months; HR 0.53; 95% CI: 0.44, 0.65,  $p$ -value  $< 0.0001$ ).

### 7.2 Rationale

According to local regulation, regulatory post-marketing surveillance study is required for new medicines approved in Korea to collect safety and effectiveness data in a routine clinical practice.

Korea Risk management plan (K-RMP) of Kyprolis® includes this study as a part of pharmacovigilance plan.

### **7.3 Statistical Inference (Estimation or Hypothesis [es])**

There is no formal hypothesis to be tested. Instead, the proposed study will provide descriptive data on real-life use of Kyprolis® and adverse event occurrence in patients in Korea. While the study does not target any specific patient sub-populations, it will collect data on patient characteristics with respect to “important missing information for safety” in MFDS.

## **8. Research Question and Objectives**

To obtain the safety information and effectiveness of the product in the real-life use of Kyprolis® in Korea.

### **8.1 Primary**

The primary objective of this study is to determine the incidence of adverse events (AEs), serious AEs and adverse drug reactions (ADRs) among patients receiving Kyprolis® in real-life setting in its registered indication(s) as required by MFDS.

### **8.2 Secondary**

The secondary objective of this study is to investigate effectiveness of Kyprolis® (Overall Response Rate).

### **8.3 Exploratory Objective(s)**

The exploratory objective of this study is to identify patients characteristics associated with the safety and effectiveness of Kyprolis®.

## **9. Research Methods**

### **9.1 Study Design**

This regulatory PMS is a single-arm prospective observational study on the patients with multiple myeloma who have received at least one prior therapy and then Kyprolis® in combination with lenalidomide and dexamethasone or just with dexamethasone in real-life setting. The decision to treat a patient with Kyprolis® must be independent of the patient’s inclusion in the study. No study drug will be provided by Amgen Korea. There will be no control group. All data required for the purpose of this study will be collected during routine visits.

700 patients will be enrolled to meet the minimum requirement (600 patients for safety analysis) of MFDS. The safety assessment will be performed at 4 week, 8 week, 12 week and 24 week. The objective response assessment will be performed per routine

clinical practice and captured at 12 week and 24 week. (Refer to [Table 3](#) for details.)  
Monitoring of adverse events (AEs) will continue until last follow-up visit (28 days after last injection or 24W after initial prescription of Kyprolis®). The given re-examination period is 6 years from the time of product approval.

## **9.2 Setting and Study Population**

Patients prescribed with Kyprolis® in accordance with the approved Korean prescribing information at participating medical institutions will be enrolled in this study. Prior to enrolling patients, investigators should consult the full prescribing information for Kyprolis® and familiarize themselves with the safety information in the product package label. (Kyprolis is indicated in combination with lenalidomide and dexamethasone or just with dexamethasone for the treatment of patients with multiple myeloma who have received at least one prior therapy).

### **9.2.1 Study Period**

Enrollment Period : 5 year from the time of product approval

Data Collection Period : 6 year from time of product approval

### **9.2.2 Selection and Number of Sites**

This study will be performed using consecutive registration method for patient enrolment. After a study contract is signed, the study investigator shall, until the contracted number of cases is reached, consecutively enroll the patients who are naïve to the Kyprolis® and will start to receive the study drug.

To be eligible for the study, medical institutions which have adopted or purchased Kyprolis will be selected as PMS sites.

About 40 nation-wide medical institutions, either general hospitals or cancer centers, will participate in this study and recruit patients. The centers will be asked to recruit patients consecutively wherever possible. Korean medical team reviews candidate investigators. Finally appropriate clinical sites will be selected and reviewed by functional review process in medical team in accordance with local operational instruction.

Approved

### 9.2.3 Patient/Healthcare Professional Eligibility

#### 9.2.3.1 Inclusion Criteria

A patient can be included into the study only if all of the following criteria are met:

1. Signed and dated informed consent
2. Patients diagnosed with multiple myeloma who have received at least one prior therapy
3. Patients who are prescribed with Kyprolis® (in combination with lenalidomide and dexamethasone or in combination with dexamethasone) for the first time

#### 9.2.3.2 Exclusion Criteria

All contraindications specified in the local product information have to be considered. In addition, patients treated with any regimens not specified in the approved prescribing information of Kyprolis® in Korea should be excluded from the study.

#### 9.2.4 Matching

No matching is used.

#### 9.2.5 Baseline Period

The baseline data (eg, laboratory tests, concurrent medication, number of prior lines, cytogenetic risk, ISS, prior medication for multiple myeloma, etc.) will be collected before initial injection of Kyprolis®.

#### 9.2.6 Study Follow-up

Each patient is followed-up at monthly visits for the first three months and then a follow-up visit at 6 months. Only safety data is collected during the first two monthly follow-up visits.

The end of follow-up for each patient is defined as death, loss to follow-up (eg, patients transferring to another clinic), 28 days from the last injection of Kyprolis® or 24 weeks after initial prescription of Kyprolis®, whichever occurs first.

\* For the combination regimen with lenalidomide and dexamethasone, administer Kyprolis® intravenously as a 10-minute infusion on two consecutive days, each week for three weeks followed by a 12-day rest period as shown in [Table 1](#). Each 28-day period is considered one treatment cycle.

For the combination regimen with dexamethasone, administer Kyprolis® intravenously as a 30-minute infusion on two consecutive days, each week for three weeks followed by a 12-day rest period as shown in [Table 2](#). Each 28-day period is considered one treatment cycle.

Approved

**Table 1. Kyprolis® in Combination with Lenalidomide and Dexamethasone**

	Cycle 1										
	Week 1			Week 2			Week 3			Week 4	
	Day 1	Day 2	Days 3-7	Day 8	Day 9	Days 10-14	Day 15	Day 16	Days 17-21	Day 22	Days 23-28
Kyprolis® (mg/m  )	20	20	-	27	27	-	27	27	-	-	-
Dexamethasone (mg)	40	-	-	40	-	-	40	-	-	40	-
Lenalidomide	25 mg daily on Days 1-21									-	-
	Cycles 2 to 12										
	Week 1			Week 2			Week 3			Week 4	
	Day 1	Day 2	Days 3-7	Day 8	Day 9	Days 10-14	Day 15	Day 16	Days 17-21	Day 22	Days 23-28
Kyprolis® (mg/m  )	27	27	-	27	27	-	27	27	-	-	-
Dexamethasone (mg)	40	-	-	40	-	-	40	-	-	40	-
Lenalidomide	25 mg daily on Days 1-21									-	-
	Cycles 13 and later a										
	Week 1			Week 2			Week 3			Week 4	
	Day 1	Day 2	Days 3-7	Day 8	Day 9	Days 10-14	Day 15	Day 16	Days 17-21	Day 22	Days 23-28
Kyprolis® (mg/m  )	27	27	-	-	-	-	27	27	-	-	-
Dexamethasone (mg)	40	-	-	40	-	-	40	-	-	40	-
Lenalidomide	25 mg daily on Days 1-21									-	-

a Kyprolis® is administered through Cycle 18; lenalidomide and dexamethasone continue thereafter.

Approved

**Table 2. Kyprolis® in Combination with Dexamethasone**

	Cycle 1											
	Week 1			Week 2			Week 3			Week 4		
	Day 1	Day 2	Days 3–7	Day 8	Day 9	Days 10–14	Day 15	Day 16	Days 17–21	Day 22	Day 23	Days 24–28
Kyprolis® (mg/m  )	20	20	-	56	56	-	56	56	-	-	-	-
Dexamethasone (mg)	20	20	-	20	20	-	20	20	-	20	20	-
	Cycles 2 and later a											
	Week 1			Week 2			Week 3			Week 4		
	Day 1	Day 2	Days 3–7	Day 8	Day 9	Days 10–14	Day 15	Day 16	Days 17–21	Day 22	Day 23	Days 24–28
Kyprolis® (mg/m  )	56	56	-	56	56	-	56	56	-	-	-	-
Dexamethasone (mg)	20	20	-	20	20	-	20	20	-	20	20	-

a Treatment may be continued until disease progression or unacceptable toxicity occurs.

### 9.3 Variables

Information described in [Sections 9.3.1-9.3.3](#) is collected in CRFs per a patient. CRF is used to collect data from baseline, week 4, week 8, week 12, and week 24. Adverse event and other safety information are collected throughout the follow-up period.

Approved

**Table 3. Overview of variables collected during the study**

Schedule Procedure	Initial visit	Follow-up visits (week)			Last visit 
	Kyprolis® treatment starting	4	8	12	Final assessment (at 24 weeks) or last follow-up (28 days after last injection)
Eligibility	X				
Informed consent	X				
Demographic data 	X				
Myeloma history					
Previous medical history and Concomitant disease 	X				
Diagnostic information about multiple myeloma 	X				
Visit date	X	X	X	X	X
Treatment of Kyprolis 	X	X	X	X	X
Adverse Events 		X	X	X	X
ECOG PS	X			X	X
Tumor response assessment 				X	X

1. Site name / Investigator's name, Patient's identifier / Patient's initials, Gender / Age, Height / Weight, Pregnancy
2. Date of diagnosis, international staging system (ISS) stage at study entry, site of metastasis and previous treatment regimen for multiple myeloma or number of previous treatment
3. Please refer to the detailed dose and administration schedule in [Table 1](#) and [Table 2](#).
4. AEs tracking up to 28 days after the last injection of Kyprolis® or 24 weeks after initial prescription of Kyprolis®.
5. Evaluated according to IMWG criteria. Based on the investigator's clinical assessment if a patient could not have radiological examination, , because of deterioration of medical condition
6. The last visit will occur at 28 days after the termination of treatment or the final assessment at 24W.

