### **9.7.2 Planned Method of Analysis**

#### **9.7.2.1 Analysis Populations**

The data will be analyzed using 3 patient populations: CRF-collected population, Safety population and Efficacy population. Reasons for withdrawal will be described for the withdrawn patients.

- CRF-collected population: All patients from whom CRFs have been collected
- Safety population: All patients who have received at least one dose of study product and on whom a follow-up (including telephone visit) has been conducted.
- Efficacy population: All patients who have been included in the Safety population, who also have received study product per protocol, and on whom any post-baseline efficacy evaluation has been done.

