##### 9.7.2.5 Analysis of the Primary, Secondary and Exploratory Endpoint(s)

Analysis for specified endpoints will be conducted as follows:

- Safety endpoint:  
Number of patients, subject incidence\_with adverse events, adverse drug reactions and serious adverse events during the observational period will be calculated and summarized (see [Section 11.1](#) the definition of adverse event, serious adverse event, and other safety findings to be collected).
- Effectiveness endpoint:  
Overall response rate for disease assessment - Patients with confirmed sCR, CR, VGPR, or PR will be considered to have achieved an overall response.

Approved

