**Appendix F. IMWG criteria [7]**

Response	IMWG criteria
sCR	CR as defined below plus normal FLC ratio and absence of clonal cells in bone marrow  by immunohistochemistry or immunofluorescence 
CR	Negative immunofixation on the serum and urine and disappearance of any soft tissue plasmacytomas and < 5% plasma cells in bone marrow 
VGPR	Serum and urine M-protein detectable by immunofixation but not on electrophoresis or ≥ 90% reduction in serum M-protein plus urine M-protein level < 100 mg/24 h
PR	≥ 50% reduction of serum M-protein and reduction in 24 hours urinary M-protein by ≥90% or to < 200 mg/24 h If the serum and urine M-protein are unmeasurable,  a ≥ 50% decrease in the difference between involved and uninvolved FLC levels is required in place of the M-protein criteria If serum and urine M-protein are not measurable, and serum free light assay is also not measurable, ≥ 50% reduction in plasma cells is required in place of M-protein, provided baseline bone marrow plasma cell percentage was ≥ 30% In addition to the above listed criteria, if present at baseline, a ≥ 50% reduction in the size of soft tissue plasmacytomas is also required
MR	NA
No change/Stable disease	Not meeting criteria for CR, VGPR, PR, or progressive disease
Plateau	NA
Progressive disease 	Increase of ≥ 25% from lowest response value in any one or more of the following: Serum M-component and/or (the absolute increase must be ≥ 0.5 g/dL)  Urine M-component and/or (the absolute increase must be ≥200 mg/24 h) Only in patients without measurable serum and urine M-protein levels; the difference between involved and uninvolved FLC levels. The absolute increase must be >10 mg/dL Bone marrow plasma cell percentage; the absolute percentage must be ≥ 10%  Definite development of new bone lesions or soft tissue plasmacytomas or definite increase in the size of existing bone lesions or soft tissue plasmacytomas Development of hypercalcemia (corrected serum calcium > 11.5 mg/dL or 2.65mmol/L) that can be attributed solely to the plasma cell proliferative disorder

Approved

Response	IMWG criteria

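### Table 3 note 5 lets the investigator's clinical assessment stand for tumor response when deterioration prevents radiology, although Appendix F rests response mainly on laboratory and marrow findings and the ORR counts only confirmed IMWG categories

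*Protocol*

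**What the plan says.** The tumor response row of Table 3 (Protocol, section 9.3) carries note 5. It opens with "Evaluated according to IMWG criteria" and then rests the evaluation on the investigator's "clinical assessment if a patient could not have radiological examination". The stated reason for the missing examination is "because of deterioration of medical condition". The fallback therefore has two conditions: radiology could not be done, and deterioration was the cause.

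The endpoint is defined elsewhere. Section 9.7.2.5 says "Patients with confirmed sCR, CR, VGPR, or PR will be considered to have achieved an overall response". Section 9.3.2 uses the same rule and refers to Appendix F for the categories, and the Abstract (section 4) also ties ORR to the IMWG criteria.

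Appendix F builds the categories on laboratory and marrow findings. PR, for example, requires a "reduction of serum M-protein and reduction in 24 hours urinary M-protein" of stated size, with FLC or marrow plasma cells as substitutes when M-protein cannot be measured.

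The efficacy population in section 9.7.2.1 takes patients from the safety population who were treated per protocol and "on whom any post-baseline efficacy evaluation has been done". Section 9.7.2.3 rules out imputation, and section 9.7.2.6.3 plans no sensitivity analysis.

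**The concern.** The fallback depends on whether radiology was possible, and under the Protocol's own criteria that is not usually what decides whether a response can be classified. A patient too unwell for imaging may still have M-protein and FLC results that settle the IMWG category, yet the note sends that patient to clinical judgement. The note is silent on missing M-protein, FLC or marrow data, which would actually prevent classification.

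Two errors become possible. A clinical impression of PR or better could be counted without meeting Appendix F, or a response documented by laboratory data could be overridden by a clinical impression of no response. Either would leave the ORR, the only stated secondary effectiveness measure, inconsistent with its definition. If the CRF does not record the source of each assessment, the two kinds cannot be separated at analysis.

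**Working it through.** The Protocol gives no figure on this point, so there is none to reproduce. The main check is a comparison of the text.

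**Step 1: what each response category needs in Appendix F.**

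| Category | Laboratory or marrow basis | Component that may need imaging |
|---|---|---|
| sCR | CR plus normal FLC ratio and no clonal marrow cells | as for CR |
| CR | negative serum and urine immunofixation, marrow plasma cells below 5% | disappearance of any soft-tissue plasmacytomas |
| VGPR | M-protein seen on immunofixation but not electrophoresis, or a large M-protein reduction | none stated |
| PR | serum and urine M-protein reduction, or FLC or marrow substitutes | plasmacytoma size, only if present at baseline |

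Bone lesions appear only under progressive disease and relapse. No response category is defined by clinical assessment. For a patient without plasmacytomas, missing radiology alone does not prevent assignment to sCR, CR, VGPR or PR.

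**Step 2: does another section contain the fallback?** Section 9.3.2 introduces required assessments but gives only the pointer to Appendix F. Section 9.7.2.1 does not require an IMWG-evaluable assessment. No section confines the clinical assessment to the imaging component, flags it, or keeps it out of the ORR.

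**Step 3: scale, on assumed inputs.** Let s be the share of patients assessed clinically and c the share of those called responders. Let p be the ORR in the remaining patients, and r the share of the clinically assessed patients who would be responders by IMWG. The Protocol gives none of these. Assume s = 5% or 10%, c = 50% and p = 70%.

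ORR with the clinical calls included = (1 − s) × p + s × c:
- s = 5%: 0.95 × 70% + 0.05 × 50% = 69.0%
- s = 10%: 0.90 × 70% + 0.10 × 50% = 68.0%

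The shift depends on what would happen to these patients otherwise:

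| Alternative handling | Shift | s = 5% | s = 10% |
|---|---|---|---|
| All counted as non-responders | s × c | +2.5 points | +5.0 points |
| All left out of the ORR | s × (c − p) | −1.0 point | −2.0 points |
| All classified by IMWG, r from 0% to 100% | s × (c − r) | +2.5 to −2.5 points | +5.0 to −5.0 points |

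For comparison, the 95% half-width with 600 patients (the minimum in section 9.5; the efficacy population may be smaller) is 1.96 × √(0.7 × 0.3 / 600) = 3.7 points at an ORR of 70%. With 600 patients, 6 reclassified patients move the ORR by 6/600 = 1.0 point.

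**The case against.** The strongest reply is that note 5 can be read consistently with the rest of the Protocol. It begins with IMWG, and the following sentence is a fragment that may mean only that clinical judgement replaces the imaging finding that could not be obtained. Appendix F has such findings: plasmacytomas for CR and PR, and bone lesions or plasmacytomas for progression. In a deteriorating patient the natural use would be to call progression, which adds no responders. The word confirmed in sections 9.3.2 and 9.7.2.5 could also be taken to exclude purely clinical responses. This reading is possible, but the note does not state it, and an investigator completing the CRF could reasonably do otherwise.

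The limit to deterioration also stands. A reader might infer that any patient without imaging leaves IMWG; the note does not say that. The limit makes the affected group small and probably less likely to be called responders. It does not make them all non-responders, since the note refers to medical condition rather than disease progression, and toxicity or infection can prevent imaging while the myeloma is in response.

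A reader might further infer that the ORR is inflated by 2.5 to 5 points. That requires the assumed shares and also that every such patient would otherwise count as a non-responder. The sign reverses if they would be left out.

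Finally, the study is descriptive, ORR is secondary, response is captured in routine practice, and section 9.9 acknowledges information bias. These facts limit the weight of the point but do not remove the conflict in the text.

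**Conclusion.** The point holds as a conflict within the Protocol. Read literally, Table 3 note 5 bases response on clinical assessment for a defined group of deteriorated patients, while Appendix F and sections 9.3.2 and 9.7.2.5 admit only confirmed IMWG categories. Missing radiology is the wrong trigger for most of these patients, because imaging matters to response categories only through plasmacytomas.

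The number affected is not given and is probably small. The size of any ORR shift rests on assumed shares, and its direction is not determined by the documents, so no claim of inflation is supported. A reader might also infer from section 9.7.2.1 that a clinical impression qualifies a patient for the ORR denominator. The section does not say so; it only leaves the term efficacy evaluation open. The conflict is worth correcting at any of these magnitudes, because it concerns what is recorded at the site.

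**What to change.** Reword note 5 so that:

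- response is assigned by IMWG from the available M-protein, FLC and marrow data;
- clinical assessment may replace only the imaging-dependent component (plasmacytoma, bone lesions) and is flagged on the CRF;
- a purely clinical impression does not count as sCR, CR, VGPR or PR;
- a patient who cannot be classified by IMWG is recorded as not evaluable, and the number of such patients is reported alongside the ORR.

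State how not-evaluable patients enter the ORR denominator, consistently with the efficacy population in section 9.7.2.1 and the no-imputation rule in section 9.7.2.3. Counting them as non-responders is one option, but it is a separate choice that would have to be squared with section 9.7.2.3; this point does not depend on it.

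The cost is one rewritten footnote and one CRF flag or response code. A few more patients would be reported as not evaluable, and the ORR may change slightly.
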